4.4 Substudies Entry Criteria

4.4.1 Treatment PK Substudy

In addition to meeting all entry criteria for the primary study, subjects desiring to enter the PK substudy must meet all of the following criteria:

- be 16-35 years old at the time of enrollment in the primary study

- have signed informed consent for the PK sampling prior to collection of the blood sample on day of IUS insertion
- have venous access adequate for multiple blood draws
- have not received hormonal contraception within 7 days of enrollment

4.4.2 Endometrial Thickness Substudy

In addition to meeting all entry criteria for the primary study, subjects desiring to enter the substudy assessing endometrial thickness must:

- be 16-35 years old at the time of enrollment in the primary study
- be assigned to LNG20
- have signed informed consent for the endometrial thickness assessments prior to IUS assignment

4.4.3 Elimination PK Substudy

Subjects desiring to enter the elimination PK substudy must meet all of the following criteria:

- be 16-35 years old at the time of enrollment in the primary study
- have been assigned to LNG20
- have completed 121 months of LNG20 use
- have signed informed consent for the elimination PK sampling prior to randomization for the elimination PK sampling timepoint
- not use hormonal contraception and not attempt to become pregnant during substudy participation such that the subject agrees to one or more of the following criteria:
 - sexually abstinent for up to 2 weeks
 - use of a non-hormonal method of birth control for up to 2 weeks

5. STUDY TREATMENTS

After written consent has been obtained and eligibility has been established, the subject will be assigned a subject identification number and assigned by IVRS to either LNG20 or Mirena (except those 36 to 45 years old who will only receive LNG20). The LNG20 IUS may be used for up to 121 continuous months for the LNG20 16-35 year old enrollment group, 96 continuous months for the LNG20 36-45 year old enrollment group and the Mirena IUS may be used for up to 60

continuous months. Only the assigned IUS may be inserted into the respective subject.

5.1 LNG20 IUS (Dosage and Formulation)

This T-shaped polyethylene device contains 52 mg of levonorgestrel. For further details, see the LNG20 Investigator's Brochure.

5.2 Mirena IUS (Dosage and Formulation)

This T-shaped polyethylene device contains 52 mg of levonorgestrel. For further details, see the Mirena Package Insert in the Study Reference Manual.

5.3 IUS Supply and Administration

Each IUS is packaged as a single use sterile system. Accessories that are used for IUS insertion into the uterine cavity and do not remain in permanent contact with the subject are included in the sterile package with the IUS. The IUS with the accessories should be stored in its sterile sealed package until insertion.

See the Investigator's Brochure for LNG20 product description, the Study Reference Manual for Mirena product description, and the Study Reference Manual for LNG20 and Mirena insertion and removal instructions.

5.4 IUS Storage and Accountability

LNG20 and Mirena should be stored at 25°C (77°F); with excursions permitted between 15-30°C (59-86°F) [See USP Controlled Room Temperature] prior to use. Study drug accountability, reconciliation and record maintenance are responsibilities that must be performed in accordance with all applicable regulatory requirements. All unused IUSs will be stored for inventory and collection. Storage and shipping procedures to return unused IUSs are detailed in the Study Reference Manual.

All expelled (when available) and removed IUSs will be stored and collected for analysis. Storage and shipping procedures to return removed and expelled IUSs are detailed in the Study Reference Manual.

For unsuccessful insertions all IUSs and their associated inserters will be stored at the site for potential analysis. The sponsor will notify the site which IUSs with their associated inserters will require to be shipped or may be destroyed on site. Storage and shipping procedures for unsuccessful insertion IUSs and inserters are detailed in the Study Reference Manual.

5.5 IUS Replacement

No IUSs will be replaced if an expulsion or removal occurs. No subjects will be eligible for temporary IUS removal.

5.6 Concomitant and Excluded Therapy

Concomitant medications are any prescription medications or over-the-counter preparations used by the subject between 7 days prior to enrollment (30 days for anticoagulants) and 30 days following IUS discontinuation. All concomitant medications, including excluded therapies, must be documented in the Concomitant Medication CRF. Subjects who begin to chronically use excluded therapies may require discontinuation from the study. The Medical Monitor should be contacted to discuss possible discontinuation of these subjects.

The following concomitant therapies are excluded while on study treatment:

- Hormonal contraceptives with the following exceptions:
 - An oral, transdermal, vaginal or combined monthly injectable hormonal contraceptive may be used in the first month only as outlined in Section 6.3;
 - Emergency contraception should be recommended in any situation when the subject feels the IUS expelled and she subsequently had intercourse. Subjects will not be discontinued from the study because of emergency contraceptive use.
- A previously inserted contraceptive implant, IUD or IUS unless the implant, IUD or IUS is removed prior to study IUS insertion (may be removed immediately before study IUS insertion).
- Any other contraceptive method that could obscure the efficacy parameters of this investigational contraceptive should not be used during study participation. However, if the subject feels the need to protect herself against sexually transmitted infections, she should be advised to use a male condom. If the use of a male condom becomes a regular part of the subject's contraception, the site Principal Investigator should check with the Medical Monitor

about possibly discontinuing the subject from study participation. All condom usage will be documented on the daily subject diaries.

- Any non-contraceptive estrogen, progesterone, testosterone, or gonadotropin (e.g. hCG)
- Misoprostol on day before or day of IUS insertion or removal
- Any cervical dilating instrument used during IUS insertion other than Pratt dilators, a lacrimal duct probe or an os finder
- Any investigational treatment or medication other than the LNG20.

5.7 Blinding

This is an unblinded, open-label study.

6. STUDY PROCEDURES

A flowchart of study assessments is in Appendix A.

6.1 Clinical Laboratory Tests

The site's local laboratory will be used for hematology, chemistry, quantitative hCG, Chlamydia, gonorrhea, and Pap test evaluations. High sensitivity urine pregnancy testing may be performed in the clinic. Plasma levonorgestrel samples will be obtained, processed, packaged and shipped to the central clinical lab per the instructions provided in the Laboratory Operations Manual. HIV and any other clinically appropriate STD testing are recommended per CDC guidelines for any subject with a change in sexual partner since her last examination; subjects should be referred for such testing within the local standard of care.

6.2 IUS Insertion Definitions

- An **insertion attempt** is considered to start with the assignment of the IUS in the IVRS and the opening of the LNG20 kit with the intent to perform an insertion, unless there was a notable product defect upon inspection of the product
- The **insertion procedure** is considered to have started once the speculum is placed for the purpose of IUS insertion. No instrumentation of the cervix can occur prior to contacting the

IVRS during the enrollment visit. The insertion procedure is considered to have ended with the removal of the speculum

- **IUS insertion** starts with placement of any instrument, device or needle into or on the cervix. IUS insertion ends with completion of cutting the IUS threads following successful intrauterine IUS placement
- **IUS insertion failure** is considered to occur when after contact with the external cervical os with the inserter the completion of IUS insertion is not achieved. Loss of product sterility due to clinician error is also considered a failed insertion
- **Successful IUS insertion** is considered as retention of the IUS in the uterus through the cutting of the strings; the day of successful IUS insertion is considered Study Day 1

6.3 Screening/Enrollment Visit

Screening is considered to start with the signing of the Informed Consent Form by the subject. Although the Screening and Enrollment Visits may occur during one visit, the Screening procedures may be performed over multiple days. The Enrollment Visit is considered to be on the date the subject is assigned through the IVRS. Screening test results are not required to be available prior to the Enrollment Visit.

Scheduling of the Enrollment Visit must take the following schemes into account:

- When switching from an oral, transdermal or vaginal hormonal contraceptive, the subject should continue that method after the study IUS insertion until the end of the current cycle. If using the contraceptive continuously (without a hormone free interval), then discontinue 7 days after IUS insertion. When possible, the Enrollment Visit should be scheduled during the hormone-free time of the cycle (i.e., “placebo week,” “patch-free week,” or “ring-free week”)
- When switching from an injectable monthly combined hormonal injection, the study IUS insertion may occur anytime within 28 days of the last injection
- When switching from non-hormonal contraception (except copper IUD), the study IUS insertion **must** be performed within the first 7 days of the menstrual cycle

- When switching from a contraceptive implant, another hormonal IUS, or a copper IUD, the study IUS insertion may occur anytime in the menstrual cycle but should occur on the same day as removal of the implant, non-study IUS, or IUD
- Women who need a screening Pap test (see section 6.11) should be scheduled for screening on a day they are expected to have minimal or no bleeding
- All enrollment procedures must be completed within 30 days of screening. If greater than thirty days, Medical Monitor approval must be obtained before rescreening or enrollment

6.3.1 Screening Procedures

All screening procedures must be performed before Enrollment Visit procedures. Although screening test results are not required to be available prior to the Enrollment Visit, all specimens for screening laboratory testing must be collected prior to enrollment (IVRS contact).

- Written informed consent prior to conducting any study specific procedures
- Demographic information
- Medical history, including pregnancy, contraception, menstrual cycles, and vaginal bleeding and cramping patterns
- Medication history for 7 days prior to enrollment (anticoagulant use for 30 days)
- High sensitivity urine pregnancy test (positive test would exclude subject)
- Height, weight, temperature, and blood pressure (all must be measured at the Screening Visit)
- Breast exam and any clinically indicated physical examination
- Pelvic exam, STD testing and Pap test:
 - Pelvic exam, STD testing and Pap test (if not required for eligibility) may be deferred to the time of IUS insertion if screening and enrollment visits occur on the same day and there is otherwise no clinical reason to perform the pelvic examination prior to enrollment
 - Pap test for eligibility:
 - All subjects over 20 years and 6 months old require a Pap test for eligibility from within the last 18 months (see section 6.11)

- Enrollment and IUS insertion may not occur until eligibility with a documented test is confirmed
 - Chlamydia testing for all subjects
 - Gonorrhea testing for any subject following a change in sexual partner since last tested or if never tested after change. In addition, HIV and other related sexually transmitted infection testing is recommended
- Hemoglobin, Serum creatinine, AST, ALT, and bilirubin
- Review eligibility criteria (subject failing to meet all inclusion/exclusion criteria are to be recorded as Screen Failures)

6.3.2 Enrollment Visit Procedures

Once the IVRS is contacted and an IUS is assigned, the subject is considered enrolled. Insertion of the assigned IUS must be attempted on the same day the IVRS assignment occurs. Second insertion attempts are allowed and can occur on a different day, but must be within 30 days of signing the informed consent. The day of successful IUS insertion is considered Study Day 1. Enrollment procedures and study IUS insertion must be scheduled per the guidelines outlined in Section 6.3. If screening and enrollment are occurring on the same day, all screening laboratory blood or urine testing must be collected prior to enrollment in the IVRS; cervical tests may be collected at the time of insertion.

- For women having enrollment on the same day as screening:
 - Perform all screening procedures prior to contacting the IVRS except for the pelvic exam and any cervical testing which can be performed as a continuum with the insertion procedure *EXCEPTION:* a separate pelvic exam must be completed prior to contacting the IVRS if there is clinical suspicion that anatomical issues may prevent successful insertion
- For women having enrollment on a different day than screening, include the following:
 - Repeat a high sensitivity urine pregnancy test prior to calling the IVRS
 - Review results of screening tests, if available:
 - If screening test results **are not** available prior to enrollment

- Enrollment may proceed **unless** an entry criteria Pap test result is pending (See section 6.11)
- If screening test results **are** available prior to enrollment:
 - If a Pap test was performed and meets the exclusion criteria, the subject must not be enrolled; however, she can be re-screened if entry criteria are satisfied at a future date
 - If STD testing (Chlamydia or gonorrhea) is positive, enrollment must be delayed until the subject completes appropriate antibiotic treatment
 - If tests are appropriately collected but reported unevaluable prior to enrollment or successful insertion the tests must be repeated
- Enrollment procedures:
 - Confirm eligibility criteria
 - Enroll in IVRS
 - Insert IVRS assigned study IUS using the techniques described in the Investigator's Brochure.
 - Up to two attempts for insertion can be made. Each attempt should use a new IUS of the assigned treatment group. The IVRS must be contacted before each attempt
 - If the IUS is unable to be inserted after two attempts or the uterus sounds to <5.5 cm:
 - If there are no AEs related to the insertion attempt (s), the subject will be discontinued from the study and is not required to have any subsequent study-related follow-up
 - If there are AEs related to the insertion attempt (s) the subject should be followed at appropriate intervals by clinic visit or telephone contact until the adverse event resolves or has stabilized, after which the subject can be discontinued from the study
 - Evaluate for adverse events related to IUS placement procedure
 - Dispense diaries and instruct subjects on diary completion (see Study Reference Manual)

- Instruct subjects on the following:
 - How to correctly check for the IUS string in the vagina. Subjects will not be required to routinely check for IUS placement but if a subject believes the IUS is expelled or no longer in the correct place, she can check for the IUS string if she desires.
 - Call for an urgent study visit if she:
 - Suspects she is pregnant
 - Has expelled the IUS (If IUS is retained, it should be provided to the to the study site at the visit which will be an Early Discontinuation Visit.). Subject should be instructed not to rinse the expelled IUS
 - Has symptoms of a pelvic infection
 - Does not feel the strings
 - Believes she feels the IUS in her cervix or vagina
 - If an urgent study visit is required, she should refrain from having sex or use appropriate non-hormonal contraception until a study evaluation is completed
 - Counsel regarding HIV and STD precautions
 - Schedule next appointment

6.4 Post-Insertion Study Follow-Up Visits

Post-insertion study follow-up evaluations will occur at Months 1, 3, 6, 12, 18, 24, 30, 36, 42, 48, 54, 60, 66, 72, 78, 84, 90, 96, 102, 108, 114 and 120 (LNG20 36-45 year old group only through Month 90 and Mirena subjects only through Month 54). The visits should occur within 14 days before or after the expected calendar visit date (within 7 days for the Month 1 and 3 visits).

- Diaries
 - Collect diaries and review for appropriate completion.
 - Confirm menstrual bleeding and cramping information is entered correctly (Months 1, 3, 6, 12, 18, and 24 only)
 - Confirm other contraception use is entered correctly

- Confirm compliance with study IUS by reviewing other contraception method(s) documented in diaries.
- The IUS would be considered her primary method of contraception if no regular use of other contraception is indicated on the diaries
 - Dispense additional diaries as needed
- Medical review
 - Review of adverse events or changes in medical history
 - Review of concomitant medications
 - Complete Bleeding/Cramping Form
 - All subjects: Months 30, 36, 42, 48 and 54
 - All LNG20 subjects: also Months 60, 66, 72, 78, 84
 - LNG20 16-35 year old enrollment group: also Months 90, 96, 102, 108, 114 and 120
 - Inquire about change in sexual partner
- Collection of blood sample for
 - Hemoglobin
 - All subjects: Month 12
 - All LNG20 subjects: also Month 60
 - LNG20 16-35 year old enrollment group only: Also Month 120
 - Plasma levonorgestrel
 - All subjects: Months 36, 42, 48 and 54
 - LNG20 subjects enrolled prior to 31May2011:
 - LNG20 16-35 year old enrollment group: also Months 60, 72, 84, 96, 108 and 120
 - LNG20 36-45 year old enrollment group: also Months 60, 72 and 84
- Physical examination and testing
 - High sensitivity urine pregnancy test (if positive, see Sections 7.4 and 7.5)
 - Weight and blood pressure (both must be measured at each visit)
 - Breast exam
 - All subjects: Months 12, 24, 36 and 48
 - All LNG20 subjects: also Months 60, 72 and 84

- LNG20 16-35 year old enrollment group: also Months 96, 108 and 120
- Any clinically indicated physical examination
- Clinically verify presence of IUS by palpation or direct visualization of strings (for missing strings management see Section 6.14 and Appendix C)
- Pelvic exam
 - All subjects: Months 12, 24, 36 and 48
 - All LNG20 subjects: also Months 60, 72, 84
 - LNG20 16-35 year old enrollment group: also Months 96, 108 and 120
- Pap test if indicated, see section 6.11
 - All subjects: Months 12, 24, 36 and 48
 - All LNG20 subjects: also Months 60, 72, 84
 - LNG20 16-35 year old enrollment group: also Months 96, 108 and 120
- STD testing:
 - Chlamydia testing for all subjects 25 years old or younger
 - All subjects: Months 12, 24, 36 and 48
 - All LNG20 subjects: also Months 60, 72, 84
 - LNG20 16-35 year old enrollment group: also Months 96, 108 and 120
 - Chlamydia and gonorrhea testing for any subject following a change in sexual partner since the last study visit. In addition HIV and any other appropriate STD testing should be performed as recommended by the CDC.
- Interview subject regarding future plans for relocation or discontinuation
- Month 90 visit for LNG20 36-45 year old enrollment group and Month 120 visit for LNG20 16-35 year old enrollment group: Discuss contraception options in preparation for the upcoming Discontinuation Visit such that the subject can immediately initiate another method (the site should attempt to have her desired method available) or be abstinent to:
 - Avoid conception within 7 days after IUS discontinuation
 - Enable the subject to avoid undesired pregnancy
- Schedule next appointment

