Subjects will receive detailed instructions on how to record vaginal bleeding, dysmenorrhea, and other contraceptive use in a daily diary during the first 24 months of study participation. Thereafter, only other contraceptive use will continue to be recorded daily on a diary for the remainder of study treatment in addition to the information collected at each study visit. After 24 months, bleeding and dysmenorrhea information only will be obtained for the remainder of study treatment via interviews by study staff during each study follow-up visit and contact (every 3 months) during treatment.

In addition, Levonorgestrel plasma levels will be obtained for all subjects at six month intervals and at IUS discontinuation visit beginning with Month 36 until Protocol Version 9 when thereafter, levonorgestrel plasma levels will be obtained in all subjects at IUS discontinuation and also annually in all women enrolled prior to 31May2011.

The Sponsor intends to retain all IUSs that are removed or expelled (when possible) and analyze an appropriate sample of these systems.

The following substudies will be performed at selected sites:

- Levonorgestrel PK data will be obtained in a subset of approximately 60 subjects (20 non-obese LNG20 subjects, 20 non-obese Mirena subjects and 20 obese LNG20 subjects). In

addition to all procedures outlined in Section 6 for the concomitant primary study visits, LNG plasma samples will be obtained at Enrollment (pre-IUS insertion), Weeks 1 and 2, and Months 1, 3, 6, 9, 12, 18, 24 and 30 after IUS insertion (includes three extra visits at Weeks 1 and 2, and Month 9, not included in the main study). These subjects will be required to give informed consent for participation in the levonorgestrel PK subset (See Section 4.4).

- A subset of 60 subjects assigned to LNG20 and completing 121 months of study treatment will have levonorgestrel samples obtained at various timepoints after IUS removal to characterize the LNG elimination profile. Each subject in this subset will be randomized to one timepoint (one extra visit) post-IUS removal (24 hours, 48 hours, 7 days or 14 days) such that fifteen subjects are randomized to each timepoint.
- A subset of 60 women assigned to LNG20 at selected sites will have transvaginal ultrasound evaluations at enrollment (pre-IUS insertion), 1 year, 5 years and 10 years (pre-IUS removal) to assess changes in endometrial thickness.

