6.5 Contacts Between Study Visits

Telephone or e-mail contacts for safety evaluation will occur at the end of 9, 15, 21, 27, 33, 39, 45, 51, 57, 63, 69, 75, 81, 87, 93, 99, 105, 111 and 117 months of use (LNG20 36-45 year old enrollment group only through Month 93 and Mirena subjects only through Month 57). The contacts should occur within 14 days before or after the expected contact date.

- Review of adverse events or changes in medical history
- Review of concomitant medications
- Review contraception method history since last scheduled study contact. The IUS would be considered to be her primary method of contraception if no regular use of other contraception is indicated on the diaries.
- Complete Bleeding/Cramping Form
 - All subjects: Months 27, 33, 39, 45, 51 and 57
 - All LNG20 subjects: also Months 63, 69, 75, 81, 87, 93
 - LNG20 16-35 year old enrollment group: also Months 99, 105, 111 and 117
- Inquire about change in sexual partner. If a contact elicits that there has been a change in sexual partner since the last time the subject had STD testing, she should be asked to come to the office for an Unscheduled Visit for Chlamydia and gonorrhea testing. In addition, HIV and any other appropriate STD testing should be performed as per CDC recommendations.
- Interview subject regarding future plans for relocation or discontinuation
- LNG20 subjects who are beyond the Month 90 study visit at the time that an investigative site obtains Institutional Review Board approval of Protocol Version 9.0 will be informed about the amendment changes at the Month 93 telephone contact or, if the Month 93 telephone contact has already occurred, at an additional telephone contact.

- Telephone contact prior to any early IUS discontinuation:
 - Discuss contraception options in preparation for the upcoming Discontinuation Visit such that the subject can immediately initiate another method (the site should attempt to have her desired method available) or be abstinent to:
 - Avoid conception within 7 days after IUS discontinuation
 - Enable the subject to avoid undesired pregnancy
 - Request the subject not have intercourse for at least 24 hours before the Discontinuation Visit; the visit may need to be rescheduled if the subject has intercourse within 24 hours of IUS removal
- Confirmation of next scheduled appointment

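### Protocol 6.4 omits the Month 90 Bleeding/Cramping Form for the 36-45 group, although that group attends Month 90 and Protocol 3.1 asks for the interview at every visit and contact

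*Protocol*

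**What the plan says.** Protocol 3.1 sets the general rule. Once the bleeding diary ends at Month 24, bleeding and dysmenorrhea information is obtained "via interviews by study staff during each study follow-up visit and contact (every 3 months) during treatment". The synopsis and SAP section 3 repeat this, and none of the three exempts an age group or a visit.

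Protocol 6.4 sets the visits and the form list. Post-insertion visits run "LNG20 36-45 year old group only through Month 90 and Mirena subjects only through Month 54". The visit forms are listed in three tiers:

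- The first tier applies to every woman in the study, whichever device she has: "All subjects: Months 30, 36, 42, 48 and 54".
- The second tier drops Mirena and still includes both LNG20 age groups, with the last entry at Month 84.
- The third tier is for the younger LNG20 women alone, and it is where Month 90 appears: "LNG20 16-35 year old enrollment group: also Months 90, 96, 102, 108, 114 and 120".

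Protocol 6.5 adds forms at the contacts between visits, first "All subjects: Months 27, 33, 39, 45, 51 and 57" and then, once Mirena use has ended, "All LNG20 subjects: also Months 63, 69, 75, 81, 87, 93", with later contacts for the younger group only. Protocol 6.6 adds the form at the discontinuation visit, which is Month 96 for the 36-45 group.

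**The concern.** The two instructions disagree at one point. The older group attends Month 90, and 6.4 gives it a task there: discussing contraception before the coming removal. The form list assigns the Month 90 form only to the younger group.

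The form matters in two ways. SAP 11.6.2 summarizes its answers every three months after Month 24: whether there was cramping or bleeding, the main pattern, and the worst or heaviest level. Under Protocol 7.12.1 it is also the routine prompt for entering worse bleeding or cramping on the AE CRF. SAP 11.4.2 and 11.5.2 make that CRF the only source of these events after Month 24. Safety and tolerability up to 8 years in this cohort is a stated secondary objective, and Month 90 falls in its last year.

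**Working it through.** No sample size, power or error rate is involved. The check lists the form months for each group and compares them with a 3-monthly grid.

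**Forms listed for the 36-45 group**

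- Visits (6.4): 30, 36, 42, 48, 54, then 60, 66, 72, 78, 84, giving 10 forms.
- Contacts (6.5): 27, 33, 39, 45, 51, 57, then 63, 69, 75, 81, 87, 93, giving 12 forms.
- Discontinuation visit (6.6): 96, giving 1 form.
- Total: 10 + 12 + 1 = 23.

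**Points on the grid**

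| Group | Grid | Points | Listed | Missing |
|---|---|---|---|---|
| LNG20 36-45 | Months 27 to 96 | (96 − 27)/3 + 1 = 24 | 23 | Month 90 |
| LNG20 16-35 | Months 27 to 120 | (120 − 27)/3 + 1 = 32 | 32 | none |
| Mirena | Months 27 to 60 | (60 − 27)/3 + 1 = 12 | 12 | none |

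**Does a neighboring form cover the gap?** Protocol 7.12.1 and the questions in SAP 11.6.2 set a 3-month look-back. The Month 87 form covers Months 85-87, Month 93 covers 91-93, and Month 96 covers 94-96. Months 88-90 fall in none of them. With Month 90 added, 24 of 24 points are listed and no month is uncovered.

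**Comparison within 6.4.** Month 54 is Mirena's last regular visit, the parallel position, and the form is listed there. Breast, pelvic, Pap and Chlamydia items also stop at Month 84 for LNG20 women as a whole. That is coherent for annual items, because this group's next annual point is Month 96. It is not coherent for a 3-monthly form.

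**Women still in use at Month 90 (7.5 years).** The documents give no retention figure for this cohort. As an assumption, take the annual discontinuation ceilings in Protocol 9.1, which were set for sizing the 16-35 efficacy group: 20%, 19%, 17%, then 16% per year.

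- Ceilings as stated: 150 × 0.80 × 0.81 × 0.83 × 0.84^4.5 = 150 × 0.2454 = 36.8.
- These ceilings imply ten-year retention of 0.80 × 0.81 × 0.83 × 0.84^7 = 0.159, whereas 9.1 also states 76% cumulative discontinuation, or 0.24 retained. Rescaling the hazards to 0.24 uses the factor ln 0.24 / ln 0.159 = 0.775. This gives 150 × 0.2454^0.775 = 50.5.

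The range is therefore about 37 to 50 women, each with one of four year-8 forms (Months 87, 90, 93, 96) not listed.

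**The case against.** The strongest reply is that no loss is established. A site that follows 3.1 will hold the interview at Month 90, so the documents contain two inconsistent instructions and not a settled decision to skip the form. This stands. A reader might infer that the interval is never collected, but that follows only at sites that work from the 6.4 list. Also, under 6.6 a woman who discontinues after Month 90 and before her Month 93 form has the period since her Month 87 form recorded.

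A reader might also infer that worse bleeding in the gap depends on unprompted self-report. The documents do not support that. Section 6.4 requires adverse event review at follow-up visits for every group, 7.6 makes site staff responsible for asking, and 7.12.1 sends self-reported worsening in months without a form to the AE CRF. What would be missing is the form's specific questions.

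Three further inferences also go too far:

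- The cohort does not serve safety alone. SAP 9.3 plans a Pearl Index and life tables for it, and neither uses this form.
- No trend model depends on Month 90. SAP 11.6.2 is descriptive, SAP 5.1 rules out formal testing, and 23 of 24 points remain.
- It cannot be said that most of these visits lay ahead when this version was approved in October 2017. Only overall recruitment dates are given, and 6.5 expects some LNG20 women to be past Month 90 already.

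These points limit the weight of the issue. None of them supplies routine pattern and intensity data for continuing users, and none gives a reason for omitting Month 90.

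**Conclusion.** This is a real internal inconsistency with a small effect. Protocol 3.1, the synopsis and SAP section 3 require the interview at Month 90, and the 6.4 list does not give it to the 36-45 group. Where the list is followed, Months 88-90 have no form for continuing users, and one of 24 scheduled points drops out of a descriptive safety summary. The figure of about 37 to 50 women rests on applying the 16-35 discontinuation assumptions to a cohort for which the documents give none. It should be read as an order of magnitude. The primary analysis is untouched. The pattern looks like a list-editing slip, since the same cut after Month 84 suits the annual items, but the documents do not state the cause. Whether Appendix A has the same omission cannot be read from the available text of its LNG20 grid, so no error is claimed there.

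**What to change.** In Protocol 6.4, extend the Bleeding/Cramping Form line for all LNG20 women to Months 60, 66, 72, 78, 84 and 90, and start the 16-35 line at Month 96. Check that the LNG20 schedule in Appendix A agrees. No change to SAP 11.6.2 is needed. If the omission was intended, 3.1, the synopsis and SAP section 3 should state the exception.

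The cost is one number moved between two lines, issued as a protocol change under 10.3.13. The women are already at the clinic and the form already exists, so no visit or instrument is added. Month 90 visits that took place without the form should be shown as missing at that time point in the summary.
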